2. INTRODUCTION

Gepotidacin (GSK2140944), a novel triazaacenaphthylene bacterial type II topoisomerase inhibitor, is being developed for the treatment of uncomplicated urinary tract infections (UTIs; acute cystitis). Gepotidacin has activity versus key pathogens, including drug-resistant strains associated with a range of conventional and biothreat infections. The microbiological spectrum of activity of gepotidacin includes *Escherichia coli*, the key causative pathogen of acute cystitis, *Staphylococcus saprophyticus*, and *Enterococcus faecalis*.

Gepotidacin selectively inhibits bacterial DNA replication by interacting in a unique way on the GyrA subunit of bacterial DNA gyrase and the ParC subunit of bacterial topoisomerase IV. This interaction appears to be highly specific to bacterial topoisomerases as evidenced by weak in vitro inhibition of human topoisomerase II α , supporting the selective activity of gepotidacin against the bacterial target. The novel mode of action of this new class antibacterial affords in vitro activity against most target pathogens resistant to established antibacterials, including fluoroquinolones.

2.1. Study Rationale

This study is being conducted based on the need to identify new and effective oral antibiotic treatment options for acute cystitis, as such therapies are becoming limited due to the increase of multidrug-resistant (MDR) pathogens and extended-spectrum β -lactamase (ESBL)-producing Enterobacterales pathogens, which are impacting the efficacy of currently available oral antibacterial treatment options (see Section 2.2). Two Phase II studies have been conducted and the results demonstrated that gepotidacin was efficacious in the treatment of uncomplicated urogenital gonorrhea and acute bacterial skin and skin structure infections (ABSSSIs) (see Section 5.3.3 in the investigator's brochure [IB] for details). In addition, a Phase IIa pharmacokinetic (PK) study (206899) was conducted in 22 female participants with acute cystitis that also included exploratory clinical and microbiological efficacy objectives. All 22 participants were evaluable for PK and clinical efficacy analysis. Of the 22 participants, 19 participants (86%) and 18 participants (82%) achieved symptom resolution at the Test-of-Cure (TOC) and Follow-up Visits, respectively. Eight of 22 participants (36%) who received at least 1 dose of gepotidacin had a qualifying baseline uropathogen (5 with *E. coli* isolates, 1 with a *S. saprophyticus* isolate, 1 with a *Klebsiella pneumoniae* isolate, and 1 with a *Citrobacter koseri* isolate). Of these 8 participants, 7 participants (88%) and 6 participants (75%) had a microbiological response of microbiological success (<10³ colony-forming units/mL [CFU/mL]) at the TOC and Follow-up Visits, respectively. Furthermore, of these 8 participants, 6 participants (75%) and 5 participants (63%) had a therapeutic response (combined per-participant microbiological and clinical response) of success at the TOC and Follow-up Visits, respectively. Refer to the IB for PK, safety, and additional efficacy results.

This study (212390) aims to evaluate the therapeutic response (combined microbiological and clinical efficacy per participant) of oral gepotidacin compared to oral nitrofurantoin for acute cystitis in adolescent and adult female participants.

2.2. Background

Urinary tract infections are very common, with approximately 11% of women >18 years of age experiencing at least 1 episode of acute cystitis per year [Foxman, 2000]. Of these, half will experience more than 1 recurrent episode over their lifetime [Foxman, 2000]. The peak incidence of acute cystitis occurs in young, sexually active women ages 18 to 29 years [Fihn, 2003]. The predominant uropathogens isolated in community-acquired UTIs are *E. coli* (75% to 90%) followed by *S. saprophyticus* (5% to 15%) [Stamm, 1993; Talan, 2000; Foxman, 2010]. *Klebsiella*, *Enterobacter*, *Proteus* species, and enterococci are observed in only 5% to 10% of acute cystitis [Stamm, 1993; Talan, 2000; Foxman, 2010].

Multidrug resistance, which is typically associated with nosocomial infections, has now emerged at the community level and has made treatment approaches for UTIs more difficult [Hooton, 2012; Flamm, 2014; Sanchez, 2016]. This has led to increasing patient morbidity, increasing costs due to reassessment and retreatment, higher rates of hospitalization, and increased use of broad-spectrum antibiotics [Foxman, 2002; Gupta, 2011a; Hooton, 2012]. Furthermore, ESBL-producing *Enterobacteriaceae* (now recognized as Enterobacterales), which includes *E. coli*, is recognized as a serious threat by the Centers for Disease Control and Prevention (CDC) [CDC, 2019] and drug-resistant *Enterobacteriaceae* is a critical priority pathogen for the World Health Organization (WHO) [WHO, 2017]. One reason for this serious threat level is the growing rise in the MDR *E. coli* sequence type (ST)-131 clone [Johnson, 2012; Nicolas-Chanoine, 2014]. Spread of this ST-131 clone has led to UTIs and blood stream infections caused by MDR *E. coli* worldwide [Peirano, 2010]. The availability of oral antimicrobials that are effective against ESBLs is limited and, for some outpatient infections, no oral options remain.

An in vitro evaluation of antimicrobial resistance of urinary *E. coli* isolates (n=12,253,679) among US outpatients between 2000 and 2010 was conducted using The Surveillance Network and found significant increases in the percentage of *E. coli* that were resistant to ciprofloxacin (3% to 17.1%) and trimethoprim-sulfamethoxazole (TMP-SXT) (17.9% to 24.2%), whereas there were minimal changes in the percentage of resistance to nitrofurantoin (0.8% to 1.6%) and ceftriaxone (0.2% to 2.3%) over time [Sanchez, 2012]. Another surveillance study, which looked at US susceptibility patterns and ESBL rates of *E. coli* from UTIs, showed an increase in ESBL rates from 7.8% to 18.3% (p<0.0001) from 2010 to 2014 [Lob, 2016]. The expansion of ESBL-producing *E. coli*, which are usually co-resistant to TMP-SXT and fluoroquinolones, is of urgent concern globally as well [Oteo, 2010]. Recent global surveillance data of *E. coli* showed high resistance rates to third-generation cephalosporins and fluoroquinolones in all 6 WHO regions [WHO, 2014]. An evaluation of the prevalence and susceptibility of acute cystitis pathogens in 9 European countries and Brazil from 2003 to 2006 showed that >10% of *E. coli* strains were MDR and 1.7% were ESBL producers [Schito, 2009]. A separate study in Brazil reported a prevalence of 7.6% ESBL-producing Enterobacterales among pathogens from community-acquired UTIs [Abreu, 2013]. In China, the prevalence of ESBLs in urinary *E. coli* in women ranged from 5% to 10.6% depending on the age group [Ho, 2007].

Based on these resistant pathogen trends, guidelines for acute cystitis now recommend first-line antibiotic treatment with nitrofurantoin, TMP-SXT, fosfomycin, or pivmecillinam, assuming the drug is available, and the patient does not have a concerning allergy history or tolerance issues [Gupta, 2011b]. Trimethoprim-sulfamethoxazole should not be used as a first-line treatment if the prevalence of resistance exceeds the 20% threshold or if TMP-SXT was used for treatment of a UTI in the previous 3 months. If any of these are concerns for a patient, then fluoroquinolones or β -lactams are recommended.

Gepotidacin is a first-in-class, novel triazaacenaphthylene antibacterial that has demonstrated in vitro activity against uropathogens including *E. coli* (see Section 4.2.1.2 of the IB for details) and provides high and sustained urine concentrations for the treatment of UTIs. With its unique ability to selectively inhibit bacterial DNA replication by a means not utilized by any currently approved human therapeutic agent, gepotidacin warrants further study as a potential opportunity to address an unmet medical need by providing a new and effective oral treatment option for acute cystitis.

A detailed description of the chemistry, pharmacology, efficacy, and safety of gepotidacin is provided in the IB. Details on the active comparator in this study, nitrofurantoin, may be found in the locally approved prescribing information.

2.3. Benefit/Risk Assessment

More detailed information about the known and expected benefits and risks and reasonably expected adverse events (AEs) of gepotidacin and nitrofurantoin may be found in the IB and the locally approved prescribing information, respectively.

2.3.1. Risk Assessment

Potential Risk of Clinical Significance	Summary of Data/Rationale for Risk	Mitigation Strategy
Gepotidacin (GSK2140944)		

Cardiovascular Effects
 
Based on nonclinical data, cardiovascular effects were reversible increase in heart rate and blood pressure (dog and monkey); reversible 10 to 21 msec (4% to 9%) increase in QTc (monkey); and at the highest dose, a reversible 2 to 3 msec (6% to 8%) increase in QRS (monkey).
 
Based on a thorough QTc clinical study, gepotidacin may cause mild, reversible heart rate effects and QT prolongation.
	
In a thorough QTc study, infusion of gepotidacin at doses of 1000 and 1800 mg over 2 hours caused a mild increased heart rate effect of approximately 6 to 10 bpm and QT prolongation measured as $\Delta\Delta\text{QTcF}$ of 12 to 22 msec. The QT prolongation evolved during the infusion and was quickly reversed over 2 hours after the end of the infusion (see Section 5.2.6 and Section 6 of the IB).
 
In Phase I and II studies, concentration-dependent QT prolongation has been observed during clinical trials with gepotidacin; however, this increase has not translated into clinically significant QTc values or changes from baseline (change from baseline >60 msec or QTcF >500 msec) or cardiovascular AEs.
 
In Phase I and II studies, gepotidacin did not have a clinically relevant effect on cardiac conduction (PR and QRS intervals).
	
See Section 5.2 for excluded cardiac conditions. Close monitoring of clinical parameters and AEs (Section 1.3) will be conducted, and treatment monitoring and evaluation criteria (Section 7.1.2) will be utilized to mitigate cardiovascular effects.
 
Participants taking medications known to increase QT or potent CYP3A4 inhibitors will be excluded (see Section 6.5.2).
 
See also the Renal and Hepatic sections within this table below.

Potential Risk of Clinical Significance	Summary of Data/Rationale for Risk	Mitigation Strategy

Gastrointestinal Effects
 
Based on nonclinical data, gastrointestinal effects were mild ulceration of the nonglandular mucosa and minimal erosion and/or mural inflammation of the glandular mucosa in stomach (rat, oral study); moderate cecal ulceration and minimal colonic erosion (rat, IV study); and vomiting (dog).
 
Lower gastrointestinal effects (soft stools, flatulence, and diarrhea) are among the most common AEs reported in gepotidacin clinical studies. Nausea and vomiting AEs have also been commonly observed in gepotidacin clinical studies.
	
See also the Acetylcholinesterase Inhibition section within this table below.
 
Clostridium difficile-associated diarrhea has been observed in clinical trials with gepotidacin.
	
See Section 5.2 for excluded medical conditions. Close monitoring of clinical parameters and AEs (Section 1.3) will be conducted to mitigate and assess gastrointestinal effects.
 
Suspected C. difficile infection will be managed according to a prespecified algorithm provided in Appendix 1.

Potential Risk of Clinical Significance	Summary of Data/Rationale for Risk	Mitigation Strategy

Acetylcholinesterase Inhibition
 
In vitro testing showed gepotidacin to be a rapidly reversible inhibitor of acetylcholinesterase in the clinical plasma concentration range.
 
Based on clinical data, caution should be used in participants who have a condition requiring treatment with anticholinergic medications or who have certain medical conditions that may be exacerbated by the acetylcholinesterase inhibition activity of gepotidacin.
	
Increased cholinergic effects can potentially be associated with more severe symptoms including atrioventricular block, seizure/convulsions, bronchospasm, and vasovagal syncope. No causal relationship between these events and the use of gepotidacin has been established during clinical trials to date.
 
Adverse events consistent with acetylcholinesterase inhibition, including diarrhea, nausea, vomiting, gastrointestinal cramping and pain, dyspnea, bradycardia, lacrimation, salivation, and diaphoresis/sweating have been reported during clinical trials with gepotidacin.
 
Mild and transient non-gastrointestinal AEs have been associated with C_{max} levels higher than this dosing regimen.
	
Participants who have medical conditions or require medications that may be impacted by inhibition of acetylcholinesterase will be excluded from participation in this study. See Section 5.2 for excluded medical conditions and Section 6.5.2, Prohibited Medications and Nondrug Therapies, for prohibited medications.
 
Close monitoring of clinical parameters and AEs will be conducted to assess effects potentially related to acetylcholinesterase inhibition (Section 1.3).


Hepatic Effects
 
In preclinical studies, increases in ALT, GLDH, alkaline phosphatase, and total bilirubin were observed in some rat studies of varying exposure.
	
Elevations in ALT have occurred in a few participants with pre-existing hepatitis C infection, but none were felt related to study treatment. The type and pattern of elevation in liver transaminases observed has not been suggestive of an adverse effect of gepotidacin and none were considered related to study treatment.
 
A substantial increase in C_{max} and AUC and decrease in clearance was observed in volunteer participants with severe hepatic impairment.
	
Participants with severe hepatic impairment are excluded from Phase III trials. See Section 5.2 for excluded medical conditions. Monitoring and stopping criteria liver events have been implemented.

Potential Risk of Clinical Significance	Summary of Data/Rationale for Risk	Mitigation Strategy

Renal Effects
 
In preclinical trials, mild to moderate tubular degeneration was noted in the rat and proteinuria in the dog. Proteinuria was also observed in humans.
	
No clinical evidence of renal toxicity has been seen in clinical trials to date.
 
A substantial increase in Cmax and AUC and decrease in clearance was observed in severe renal impairment/ESRD participants not on hemodialysis and in ESRD participants requiring hemodialysis (note: gepotidacin may have been administered at any time other than when receiving dialysis).
	
Participants with severe renal impairment/ESRD (including those who may require dialysis) are excluded from Phase III trials. See Section 5.2 for excluded medical conditions. Monitoring criteria have been implemented.

Potential Risk of Clinical Significance	Summary of Data/Rationale for Risk	Mitigation Strategy

Reproductive System Effects
 
Preclinical studies demonstrated that gepotidacin was not genotoxic and no drug-related malformations were observed. Although positive in vitro findings for clastogenicity, consistent with a mechanism related to mammalian topoisomerase II inhibition were found, in vivo data from rat micronucleus and COMET assays suggest that gepotidacin does not pose a genotoxic hazard to humans.
 
Gepotidacin effects on embryofetal development were limited to decreased fetal weights for male and female fetuses in rats and decreased fetal weights and increased fetal resorptions (fetal deaths) in mice, both at maternally toxic doses. These occurred at clinically relevant exposures (65 µg.h/mL in rat and 35 µg.h/mL in mouse).
	
There are no data on the use of gepotidacin in pregnant women.
	
Gepotidacin is contraindicated in pregnant or nursing mothers and women of childbearing potential who are not employing adequate contraceptive measures. See Appendix 2 for contraceptive measures and Appendix 8 for required pregnancy testing.

Potential Risk of Clinical Significance	Summary of Data/Rationale for Risk	Mitigation Strategy
Other		

Nitrofurantoin
	
The most frequent AEs possibly or probably related to oral nitrofurantoin treatment are nausea (8%), headache (6%), and flatulence (1.5%). As with gepotidacin, there is also a need to monitor for C. difficile-associated diarrhea during nitrofurantoin treatment.
 
Nitrofurantoin is contraindicated for patients with anuria, oliguria, or significant impairment of renal function; pregnant patients at term (38 to 42 weeks' gestation), during labor and delivery, or when the onset of labor is imminent; neonates under 1 month of age; and patients with a previous history of cholestatic jaundice/hepatic dysfunction associated with nitrofurantoin.
 
Rare adverse reactions that generally occur in patients receiving treatment for 6 months or longer are acute, subacute, or chronic pulmonary reactions, with potential insidious development of chronic pulmonary reactions (diffuse interstitial pneumonitis or pulmonary fibrosis, or both).
 
Peripheral neuropathy has occurred, which may be enhanced for patients with anemia, diabetes mellitus, electrolyte imbalance, vitamin B deficiency, and debilitating disease.
 
Nitrofurantoin has induced the occurrence of hemolytic anemia of the primaquine-sensitivity
	
Close monitoring of clinical parameters and AEs (Section 1.3) will be conducted, and treatment monitoring and evaluation criteria (Section 7.1.1) will be utilized to mitigate hepatic effects.
 
Because planned treatment in this study is only 5 days, the probability for adverse reactions associated with long-term use is low.
 
The exclusion criteria for this study include contraindications to nitrofurantoin use and exclude participants at risk for nitrofurantoin adverse reactions, including acute porphyria as an example of a rare genetic risk (see Section 5.2).
 
Participants with a history of sensitivity to nitrofurantoin, or components thereof, will not be allowed to enroll in the study (Section 5.2). Participant's medical history will be carefully evaluated for history of hypersensitivity.
 
Participants must agree not to use antacid preparations containing magnesium trisilicate or uricosuric drugs during study treatment (see Section 5.2).

Potential Risk of Clinical Significance	Summary of Data/Rationale for Risk	Mitigation Strategy
	
type, which appear to be linked to a glucose-6-phosphate dehydrogenase deficiency in the red blood cells of the affected patients.
 
Hepatic reactions, including hepatitis, cholestatic jaundice, chronic active hepatitis, and hepatic necrosis, occur rarely.
 
Concomitant administration of nitrofurantoin with antacids containing magnesium trisilicate reduces both the rate and extent of absorption, and uricosuric drugs, such as probenecid and sulfinpyrazone, can inhibit renal tubular secretion of nitrofurantoin.
 
Refer to locally approved nitrofurantoin prescribing information for specific details relating to nitrofurantoin.
	
Suspected C. difficile infection will be managed according to a prespecified algorithm provided in Appendix 1.
 
Precautions related to nitrofurantoin are summarized in detail in the Study Reference Manual.

bpm=beats per minute; AE=adverse event; ALT=alanine aminotransferase; AUC=area under the drug concentration-time curve; Cmax=maximum concentration; CYP3A4=cytochrome P450 enzyme 3A4; ESRD=end-stage renal disease; GLDH=glutamate dehydrogenase; IB=investigator’s brochure; IV=intravenous; $\Delta\Delta QTcF$ =placebo-corrected change from baseline in corrected QT interval using the Fridericia formula; QTc=corrected QT interval; QTcF=interval corrected for heart rate according to Fridericia’s formula.

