9.4.3. Safety Analyses

All safety analyses will be performed on the Safety Population. The severity of AEs and SAEs will be determined by the investigator according to the US National Institute of Allergy and Infectious Diseases Division of Microbiology and Infectious Diseases (DMID) criteria for adult toxicity assessment [DMID, 2007a], with the exception of serum creatinine adolescent laboratory data, which will be assessed using pediatric toxicity criteria [DMID, 2007b] (Appendix 13). All reported AEs will be coded using MedDRA and summarized by system organ class and preferred terms.

Estimands/Endpoints	Statistical Analysis Methods
Secondary	
 The safety endpoint will use a treatment policy strategy for the ICE of withdrawal from treatment, as safety will be assessed at all postbaseline assessments irrespective of whether the participant completed the treatment.

Estimands/Endpoints	Statistical Analysis Methods
	
 • The number and percentage of treatment-emergent AEs, study treatment-related AEs, deaths, SAEs, and AEs leading to study treatment or study withdrawal will be provided. • Treatment-emergent AEs will be summarized by severity. • Change from baseline over time in laboratory parameters, ECGs, and vital signs will be summarized with descriptive statistics. Note: Electrocardiograms will be centrally overread for the data analysis. • The frequency of laboratory abnormality events along with the shift from baseline to the worst-case postbaseline value will be provided. Abnormal liver chemistry results will be determined using increases above the upper limit of normal. Change from baseline values will be summarized with descriptive statistics. • The severity of specified AEs and laboratory abnormalities will be graded according to the modified DMD toxicity grading system (Appendix 13). Data will be tabulated and reported by absolute grade for Grades 3 and higher and shift tables, as appropriate. • Adverse events of special interest will include CV, gastrointestinal, and C. difficile infection or colitis events. In addition, AEs associated with acetylcholinesterase inhibition are also considered special interest. As described in the RAP, manual and programmatic reviews of AEs/preferred terms will be used to assess these events.

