8.3. Clinical Laboratory Analyses

Laboratory evaluations including the analyses of chemistry laboratory tests, hematology laboratory tests, urinalysis, and liver function tests will be based on GSK Core Data Standards.

For adults, laboratory abnormalities will be graded according to the modified DMID criteria [[DMID, 2007a](#)]. For adolescent participants over 12 years of age and less than 18 years of age, the adult DMID will be applied for all laboratory parameters with the exception of serum creatinine, which will be programmatically graded according to the modified DMID criteria for pediatric participants [[DMID, 2007b](#)].

Summaries of change from baseline values over time for clinical chemistry and hematology tests will be provided in separate Tables.

Abnormal liver chemistry results will be summarized by increasing folds above the upper limit of normal (ULN) including tests of interest and thresholds as follows:

- ALT or AST > 3xULN and Total Bilirubin > 2xULN
- ALT or AST > 3xULN and ALP < 2xULN and Total Bilirubin ≥ 2xULN
- ALT or AST > 3xULN and Total Bilirubin > 1.5xULN
- $(\text{ALT}/\text{ALT ULN})/(\text{ALP}/\text{ALP ULN}) > 5$ and ALT > 3xULN *
- ALT or AST ≥ 20xULN
- ALT or AST ≥ 10xULN
- ALT or AST ≥ 8xULN

- ALT or AST \geq 5xULN
- ALT or AST \geq 3xULN
- ALT \geq 20xULN
- ALT \geq 10xULN
- ALT \geq 8xULN
- ALT \geq 5xULN
- ALT \geq 3xULN
- AST \geq 20xULN
- AST \geq 10xULN
- AST \geq 8xULN
- AST \geq 5xULN
- AST \geq 3xULN
- Total Bilirubin $>$ 2xULN
- Total Bilirubin $>$ 1.5xULN

*: sign of hepatocellular injury, ALT and ALP values must occur on the same day.

Maximum post baseline total bilirubin vs maximum post-baseline ALT will be plotted as well as participant profile for liver function tests.

Urinalysis results will be summarized using descriptive statistics.

Clinical chemistry, hematology, and urinalysis test results with toxicity grade 3 or higher will be listed in separate listings.

The severity of renal impairment will be evaluated and presented according to the method previously described in Section 6.1.2.

The details of data displays are presented in [Appendix 9](#).

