3.19	Safety	AE5B	Summary of Acetylcholinesterase-Inhibition Adverse Events of Special Interest by Number of Events and Unique Preferred Term	a Table to summarize the number and % of patients experiencing 1, 2, 3, 4, 5 or more events and 1,2,3,4,>=5 or more distinct PTs.	SAC	SAC
3.20	Safety	AE5B	Summary of Acetylcholinesterase-Inhibition Adverse Events of Special Interest by Number of Events and Unique Preferred Term and Age	subgroup age group	SAC	SAC
3.21	Safety		Summary of Onset, Duration and Lag Time of AChE-I Event	a summary Table to present the statistics (mean, median, max, min) of time to first event, duration, and lag time since last dose for AchEI, non-GI AchEI, and GI AchEI events	SAC	SAC
3.22	Safety		Summary of Onset, Duration and Lag Time of AChE-I Event by Age	subgroup age group	SAC	SAC
3.23	Safety	AE5B	Summary of Adverse Events Leading to Discontinuation of Study Treatment or Withdrawal from Study by System Organ Class and Preferred Term and Maximum Grade		SAC	SAC
3.2301	Safety	AE5B	Summary of Adverse Events Leading to Discontinuation of Study Treatment by System Organ Class and Preferred Term and Maximum Grade		SAC	SAC

Safety: Tables						
No.	Population	IDSL / Example Shell	Title	Programming Notes	Deliverable	
					If study stops	If study continues
Laboratory						
3.24	Safety	LB1	Summary of Clinical Chemistry Values Change from Baseline		SAC	SAC
3.25	Safety	LB2	Summary of Emergent Chemistry Laboratory Results by Maximum Grade Increase from Baseline		SAC	SAC
3.26	Safety	LB1	Summary of Hematology Change from Baseline		SAC	SAC
3.27	Safety	LB2	Summary of Emergent Hematology Laboratory Results by Maximum Grade Increase from Baseline		SAC	SAC
3.28	Safety	LIVER1	Summary of Liver Monitoring/Stopping Event Reporting		SAC	SAC
3.29	Safety	UR3	Summary of Urinalysis Results		SAC	SAC
3.30	Safety	LIVER10	Summary of Hepatobiliary Laboratory Abnormalities		SAC	SAC

Safety: Tables						
No.	Population	IDSL / Example Shell	Title	Programming Notes	Deliverable	
					If study stops	If study continues
Vital Signs						
3.31	Safety	VS3	Summary of Worst-Case Vital Signs Results Relative to Potential Clinical Importance Criteria Post-Baseline Relative to Baseline		SAC	SAC
3.32	Safety	VS1	Summary of Change from Baseline in Vital Signs		SAC	SAC
3.33	Safety		Summary of Maximum Actual and Change from Baseline for Electrocardiogram Parameter Corrected QTc Interval		SAC	SAC
Family History						

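### The protocol promises laboratory shifts from baseline to worst postbaseline value, but the SAP plans no urinalysis shift or grade-increase table, although proteinuria is a named human finding

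*Protocol*

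**What the plan says.** **Protocol.** The renal row of Section 2.3.1 reports tubular degeneration in the rat and proteinuria in the dog, then "Proteinuria was also observed in humans". The same row says "No clinical evidence of renal toxicity has been seen in clinical trials to date". Section 3 makes change from baseline in clinical laboratory tests part of the secondary safety endpoint. Section 9.4.3 commits to the following: "The frequency of laboratory abnormality events along with the shift from baseline to the worst-case postbaseline value will be provided". A later bullet there limits graded shift tables to where they are appropriate, but this sentence carries no such limit. Appendix 8 (Table 15) lists dipstick protein and blood among the required safety tests. The Schedule of Activities collects urinalysis at Baseline, On-therapy and TOC.

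**SAP.** Section 8.3 reads: "Summaries of change from baseline values over time for clinical chemistry and hematology tests will be provided in separate Tables". For urine it says "Urinalysis results will be summarized using descriptive statistics", and it promises a listing of results at Grade 3 or above. In Section 11.9.9, Table 3.25 is the "Summary of Emergent Chemistry Laboratory Results by Maximum Grade Increase from Baseline" and Table 3.27 is its hematology counterpart. The only urinalysis table is 3.29 (shell UR3), and Section 11.9.11 adds Listing 40 of urinalysis data. Section 11.7.1.1 grades proteinuria from 1 to 4: 1+ is Grade 1, 2+ to 3+ is Grade 2, and 4+ is Grade 3. Section 2.1, which lists departures from the protocol's analysis plan, does not mention urinalysis.

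**The concern.** Inclusion criterion 3 (protocol Section 5.1) requires nitrite or pyuria, so every participant enters with an abnormal urine finding. Some will plausibly also have protein or blood on the dipstick because of the infection, and that should clear with cure. This is the laboratory panel in which baseline status matters most, and it is the one panel without a planned change or grade-increase table.

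At stake is how well the trial can describe the one renal finding that the protocol names in humans. If postbaseline protein results are summarised without reference to baseline, persisting and new abnormalities are added together. A difference between arms in new, mild proteinuria is then diluted. The reduction from what Section 9.4.3 promises is also undeclared, so a reader of the study report would not know that a protocol commitment had been narrowed.

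**Working it through.** The plan states no figure to reproduce. The check is a comparison of documents, followed by an illustration.

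**1. Planned tables by panel (SAP Section 11.9.9)**

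| Panel | Change from baseline | Maximum grade increase | Results summary |
|---|---|---|---|
| Chemistry | 3.24 | 3.25 | – |
| Hematology | 3.26 | 3.27 | – |
| Urinalysis | none | none | 3.29 |

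The data for a shift exist (one baseline and two scheduled postbaseline samples), and so does the grading scale.

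**2. What overall rates can and cannot show.** Let *b* be the proportion abnormal at baseline and *p* the proportion abnormal afterwards. The proportion of all participants who are newly abnormal, *E*, is bounded only by

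max(0, *p* − *b*) ≤ *E* ≤ min(*p*, 1 − *b*).

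- *b* = *p* = 20%: *E* lies anywhere from 0% to 20%.
- *b* = *p* = 30%: *E* lies anywhere from 0% to 30%.

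So rates before and after treatment, taken alone, do not identify emergent proteinuria within an arm.

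**3. Dilution of the comparison between arms (illustration).** The documents give no proteinuria rates, so all rates here are assumptions:

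- 1250 per arm, which is half of the approximately 2500 planned (fewer if the trial stops at the interim analysis);
- *b* from 10% to 40%;
- half of baseline-positive participants still positive afterwards, equally in both arms;
- new proteinuria in 2% of baseline-negative participants on nitrofurantoin, against 4% or 5% on gepotidacin.

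The overall postbaseline rate is *b* × 0.5 + (1 − *b*) × *e*, where *e* is the new-proteinuria rate. At *b* = 20% this gives 0.10 + 0.8 × 0.02 = 11.6% against 0.10 + 0.8 × 0.05 = 14.0%. The baseline-negative comparison is 2% against 5% in 1250 × 0.8 = 1000 per arm.

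Power (two-sided 0.05, normal approximation) is Φ[(|d| − 1.96 × SE0)/SE1], where d is the difference in rates, SE0 uses the pooled rate and SE1 the separate rates:

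| *b* | 2% v 5%: overall rates | 2% v 5%: baseline-negative | 2% v 4%: overall rates | 2% v 4%: baseline-negative |
|---|---|---|---|---|
| 10% | 69.4% | 97.2% | 39.3% | 79.4% |
| 20% | 43.5% | 95.5% | 22.8% | 74.6% |
| 30% | 28.2% | 92.8% | 15.1% | 68.9% |
| 40% | 19.1% | 88.6% | 10.9% | 62.2% |

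Lower persistence weakens the dilution but does not remove it. With 20% persistence and *b* = 40%, the overall rates are 0.4 × 0.2 + 0.6 × 0.02 = 9.2% and 0.4 × 0.2 + 0.6 × 0.05 = 11.0%. Power is then 32.0%, against 88.6% in baseline-negative participants.

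Under equal persistence the overall comparison is still valid. Its expected difference is (1 − *b*) times the difference in new-proteinuria rates. What it loses is precision.

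**The case against.** The strongest reply is that a proteinuria signal has other routes to notice, and it largely stands against any claim that the signal would go unseen. Listing 40 holds participant-level urinalysis data, and its title carries no grade restriction. Grade 3 or higher results are to be listed. Clinically significant laboratory changes are recorded as adverse events (protocol Section 8.2.4, Appendix 11) and tabulated by arm. These routes are weak for mild proteinuria, however. A listing is not a comparison, and findings attributed to the underlying disease are not adverse events unless more severe than expected.

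Second, shell UR3 is not shown. A by-visit layout is an inference, and a layout that crosses results with baseline cannot be excluded. This stands, so the point is confined to what the section text and the table titles commit to.

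Third, renal safety is covered elsewhere. Creatinine and blood urea nitrogen are in the chemistry panel and so fall under Tables 3.24 and 3.25. SAP Section 8.3 also presents renal impairment category by creatinine clearance. This stands and limits the gap to urine protein and blood.

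Fourth, new protein at TOC may reflect persisting or recurrent infection, so a shift table would not isolate a drug effect. This also stands. The table should be read as a randomized comparison between arms.

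Fifth, graded shift tables are promised only as appropriate, and protocol Section 9.4 leaves technical detail to the SAP. That softens the inconsistency, but the worst-case shift sentence itself is unqualified.

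A reader might also set the renal row's wording, "See Section 5.2 for excluded medical conditions. Monitoring criteria have been implemented", against Section 7.1, which holds no renal criterion, and infer a contradiction. The documents do not support that. The row does not cite Section 7.1, which concerns stopping treatment. It speaks of monitoring only, where the hepatic row speaks of monitoring and stopping. At most a cross-reference is missing.

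**Conclusion.** The point holds as a gap between protocol and SAP in one laboratory panel. The protocol promises baseline-to-worst shifts without excepting urinalysis. The SAP plans change and grade-increase tables for chemistry and hematology only, and Section 2.1 is silent on the difference. No listed table is titled as separating new or worsening proteinuria from abnormality present at baseline.

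The size is unknown. The power figures rest wholly on assumed baseline, persistence and emergence rates and on full enrolment. They show the direction and plausible extent of the dilution and are not an estimate for this trial. A reader might infer that drug-induced proteinuria would escape detection, or that renal safety is unmonitored. The documents support neither, given the listings, adverse event reporting and serum-based renal outputs, and the statement that no clinical renal toxicity has been seen. The change is still worth making because the finding is named, the population enters with abnormal urine, and the remedy is nearly free.

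**What to change.** In SAP Sections 8.3 and 11.9.9, add a table on the Safety Population: *Summary of Emergent Urinalysis Results (Proteinuria, Hematuria) by Maximum Grade Increase from Baseline*. Use the LB2 shell of Tables 3.25 and 3.27 and the grades in SAP Section 11.7.1.1. Add a footnote that abnormalities at TOC may reflect persisting infection, so the table is read between arms. If the sponsor prefers not to add it, record the omission and the reason in SAP Section 2.1.

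The cost is one extra table. No new data collection is needed, the shell exists, and the grades are already defined. The primary analysis and the error rate are unaffected.
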